8 OBJECTIVES AND ENDPOINTS

	Objective	Endpoint	Analysis		
Primary	To assess the safety of the PEP _{IDH1M} vaccine alone and in combination with adjuvant TMZ and/or XRT/TMZ in adult patients with progressive, resectable WHO grade II gliomas that are confirmed Grade II or transition to a higher grade glioma at the time of surgery.	The percentage of patients who experience an unacceptable toxicity defined as any Grade 3 toxicity at least possibly attributed to the vaccine (or vaccine + TMZ and/or RT) that does not resolve to baseline within 3 weeks, any Grade 3 hypersensitivity reactions requiring steroids, any Grade 4 toxicity, including neurologic events not due to progressive disease, or any life threatening-event not attributable to concomitant medication, co-morbid event, or disease progression.	See Section 15.4		
Secondary	To assess the immunogenicity of the PEP _{IDH1M} vaccine with adjuvant TMZ using ELISpot.	Mean difference in the number of SFC per 10 ⁶ lymphocytes for cells cultured with and without IDH1 peptide	See Section 15.5		
Exploratory	To describe PFS and OS.	Proportion of patients alive without disease progression 6 months after initial vaccine treatment; median progression- free survival and median overall survival.	See Section 15.6		
Exploratory	To determine if ELISpot results after vaccination predict PFS or OS.	Number of SFC per 10 ⁶ lymphocytes above pre-vaccine baseline is a predictor of PFS or OS	See Section 15.6		
Exploratory	To estimate radiographic response rate prior to surgical resection and PFS after resection using RANO criteria.	Proportion of patients with radiographic response (complete + partial response) observed prior to surgical resection. Proportion of patients alive without disease progression 6 months after resection.	See Section 15.6		
Exploratory	To determine if tumors are IDH1 negative by immunohistochemical analysis and microarray analysis at the time of post-vaccine surgery.	Proportion of tumors that are IDH1 negative at the time of surgery	See Section 15.6		
Exploratory	To characterize immunologic cell infiltrate in tumors at the time of post-vaccine surgery.	Median number of immunologic cell infiltrates at the time of surgery	See Section 15.6		
Exploratory	To determine if tumor-specific circulating DNA containing the c.395G>A (R132H) mutation can be detected in plasma before, during, and after study drug treatment.	Detection of tumor-specific circulating DNA containing R132H mutation. Mean changes in R132H mutation from baseline.	See Section 15.6		
Exploratory	To determine if 2-HG, a metabolite specifically produced by tumors with IDH R132H, can be detected in plasma by mass spectrometry before, during, and after study drug treatment.	Detection of 2-HG in plasma. Mean changes in 2-HG in plasma from baseline.	See Section 15.6		
Exploratory	To explore the impact of PEP _{IDH1M} vaccination on genetic alternations, differential protein expressions or post-translational modifications (PTMs) using quantitative proteomic strategies in patient-derived samples.	Changes between baseline and surgery in genetic alternations, differential protein expressions and post-translational modifications (PTMs)	See Section 15.6		

Table 1. Objectives and Endpoints

Exploratory	To demonstrate quantitative repeatable measures of metabolism change in IDH1+ gliomas via a standardized MRS protocol, patients will be scanned on the research MR scanner to establish same-day and longitudinal metabolite coefficient of variance and possible longitudinal metabolite changes.	Difference in levels of metabolism measured at same assessment. Changes from baseline in metabolism levels at each follow-up assessment.	See Section 15.6
-------------	---	---	------------------

9 INVESTIGATIONAL PLAN

9.1 Study Design

Subjects with radiographic and/or clinical progressive and resectable Grade II glioma with expression of IDH1^{R132H} from the primary tumor (initial diagnosis) will be enrolled after signing informed consent. After consent has been signed, **all** subjects will undergo standard of care vaccination with 0.5 mL of Td (tetanus and diphtheria toxoids adsorbed) intramuscularly (I.M.) into the deltoid muscle to ensure adequate immunity to the tetanus antigen. The tetanus vaccine will be obtained through Duke ICS Pharmacy.

Eligible subjects will undergo a 1-2 hour leukapheresis for immune monitoring. Within 48 hours of leukapheresis, subjects will receive a vaccine site pre-conditioning as a single dose of Td toxoid (1 flocculation unit, Lf, in a total volume of 0.4 mLs saline). This will be administered one day prior to receiving PEP_{IDH1M} vaccine intradermally (i.d.) to the RIGHT groin area (as described below). The peptide vaccine is administered in the groin area approximately 10 cm below the inguinal ligament as vaccine # 1. Subsequent vaccines will be given on day 15 ±3 days (vaccine #2) and day 29 ±3 days (vaccine #3). These injections will occur without TMZ. Each injection of the peptide vaccine will be given half on the right groin and half on the left groin.

Seven to 12 days after the 3rd vaccine, subjects will undergo surgical resection of tumor, which is part of the SOC for these subjects. If possible, the provider will take a photo of the injection site at the pre-op appointment seven to twelve days after the 3rd vaccine to document the subject's reaction to the vaccine. Tumor samples from the surgical resection will be evaluated as outlined in the Exploratory Objectives.

Based on tissue obtained at surgical resection, subjects with stable histologic grade at recurrence will then be treated with vaccine and adjuvant TMZ at a targeted dose of 50-100mg/m²/d for 21 days every 28 days for up to 12 cycles (please see Section 18.5 in the Appendices for TMZ). During monthly cycles of TMZ, subjects will receive the vaccine on day 22 (+ 2 days) for a maximum of 15 total vaccines (which includes the first 3 bi-weekly vaccines). Patients that have transitioned to a higher Grade brain tumor will receive TMZ and radiation therapy per standard of care and monthly vaccines.

All Adverse Events will be collected from time of consent until the end of the treatment phase of the study. The treatment phase of the study will end 1 month after the last vaccine (Section 12.3). Patients will be followed only for overall survival, progression-free survival, and subsequent therapies thereafter. For higher grade gliomas undergoing RT (please see Section 18.4 in the Appendices for SOC RT), vaccine #4 will be given during the SOC clinic visit prior to initiating RT, and vaccine # 5 will be given 4 weeks later (± 1 week) during RT. Vaccine #6 will be given at the end of RT during the SOC clinic visit to review MRI and begin post-RT TMZ, if MRI stable. Then, subjects in this treatment group will receive vaccines monthly on day 22 (+2 days) with post-RT cycles of TMZ to a maximum of 15 vaccines.

For immune monitoring and biomarker testing, subjects will have blood collected, as described in Section 12, during the following times: prior to vaccine therapy (at leukapheresis visit), prior to surgical resection (at the pre-op screening visit), prior to either RT/TMZ or first cycle of adjuvant TMZ (at SOC clinic visit) depending on tumor pathology, at vaccine # 6, and at End of Treatment (follow-up visit 1 month after vaccine #15; If a subject decides to stop participating in the study prior to vaccine #15, blood will be obtained at that time, if possible; If a subject progresses prior to vaccine #15, blood will be obtained at that time, if possible). For genomic proteomic analyses, blood and tumor samples will be obtained as described below in Section 9.4.

Subjects will be imaged with contrast-enhanced MRI according to the SOC every 10 weeks (+/- 4 weeks) while on TMZ and afterward, per the treating neuro-oncologist's recommendation. RANO criteria will be used for assessment of pseudoprogression and tumor progression (please see Section 12.7.3 for further detail). Subjects demonstrating definitive progression will be removed from study.

In addition, to demonstrate quantitative repeatable measures of 2HG in IDH1+ gliomas, subjects will be imaged using magnetic resonance spectroscopy (MRS) at baseline (prior to vaccine #1 following consent), and up to 4 times prior to surgery (please see Section 9.5 below for further information).

As part of standard care for these subjects, upon tumor progression, participants may undergo stereotactic biopsy or resection. As this is not a research procedure, consent will be obtained separately. Subjects that have this procedure done within the Duke University Health System may be approached to participate in the Duke Brain Tumor Center Biorepository study (Pro00007434). Tissue obtained from subjects who consented to the Duke Brain Tumor Center Biorepository will be used to assess immunologic cell infiltration, antigen expression, and biomarkers for immunologic response.

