9.3 Rationale for Correlative Studies

While the primary goal of this study is to assess safety of the PEP_{IDH1M} vaccine, a secondary endpoint will be to determine whether this vaccine is capable of eliciting an immune response in patients with IDH1 mutation-expressing tumor. The primary measure of immunogenicity will be by ELISpot to the immunizing peptide. For the immune system to recognize the tumor specific IDH1 mutant, this mutant peptide must be presented by human leukocyte antigens (HLA) on the surface of a tumor cell for recognition by a T cell. There are a tremendous number of HLA alleles with variable expression from person to person. As certain peptides are able to bind with much greater affinity to certain HLA alleles, the ability of one individual to present the IDH1 mutant peptide will be dependent upon their unique set of HLA alleles and may differ greatly from another individual with differing HLA. Therefore, it is critical to know the HLA type of a patient receiving the peptide vaccine as this may reveal if certain HLA types are associated with enhanced vaccine induced immune responses. Such information may suggest certain HLA types present the mutant peptide in a superior fashion and may be valuable in stratifying patients for clinical trials using this vaccine. We

intend to identify HLA types from PBMCs taken at the leukapheresis time point. The purpose of collecting these data will be to determine whether there may be immune correlates that associate with clinical outcomes such as PFS and OS following vaccination with the PEP_{IDH1M} vaccine. Although this Phase I study is not designed to be definitive towards this end, these analyses will provide the initial data necessary to adequately power future studies. Any evidence of tumor response will be determined according to the Duke PRTBTC SOP (available upon request). RANO criteria⁸² will be used for assessment of pseudoprogression. Tumor progression will need to be documented histologically, unless there are clinical contraindications, to exclude inflammatory responses presenting as radiographic or clinical changes, which could indicate potentially toxic or therapeutic responses and not tumor progression. Patients will be followed until death.

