9.6 Definition of Evaluable Subjects, On Study, and End of Study

For the initial monitoring of adverse events (see Section 15.4.2), evaluable patients will include the first 6 accrued patients who received 3 vaccinations or experienced an unacceptable toxicity due to one of the first 3 vaccinations.

For the final analysis of the primary objective (See section 15.4.2), evaluable patients will include all patients who received at least 6 vaccinations or experienced an unacceptable adverse event that was related to vaccine (or vaccine + TMZ).

Once the patient signs ICF, that subject will be considered "on study." Rationale for taking patient off protocol treatment will be documented. End of study is defined as 2 months following last vaccine for purposes of toxicity monitoring.

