12.2 Treatment Period

Patients that have consented onto this study will receive 3 vaccines as indicated above and then undergo surgical resection. Unless a patient is determined at the time of surgery to have transitioned to a higher grade brain tumor, vaccines will then continue monthly along with adjuvant cycles of TMZ on day 22 (+ 2 days) for a maximum of 15 vaccines, unless the patient has tumor progression prior to completing 12 cycles of TMZ. Subjects that have transitioned to a higher grade glioma at the time of surgery will continue on study treatment, however, they will need to undergo standard of care chemoradiation therapy. Therefore, the vaccines will be given before, during and following RT as described above. Subjects will return one month following the last vaccine for blood work (CBC and CMP) and clinical assessment to monitor for delayed toxicity.

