The PEP_{IDH1M} vaccine injections may include the risk of infection due to potential contamination of the peptides in the laboratory. This may result in localized redness, swelling, or induration at the injection site. In the most extreme situation, this may lead to systemic bacterial/fungal sepsis and possibly death. The probability of this risk is relatively low, given the small injection volume (1 mL divided between >2 intradermal locations) and the fact that the peptides will be strictly tested for sterility prior to each injection. The risk of infection due to potential contamination of the peptides in the laboratory will be minimized by biosafety quality assurance and testing. All cell cultures will be handled under sterile conditions in a core tissue culture facility dedicated to the processing of human cells. Prior to injection into patients, peptides must pass sterility tests in thiglycolate broth, tryptic soy blood agar, and inhibitory Sabouraud agar. Following injections, patients will be monitored throughout the course of the study for any signs and symptoms of infection. There have been no infections to date in the recent VICTORI (IRB #3108-05-9R4) or ACTIVATE (IRB #5421-05-1R1) clinical trials testing similar approaches in a similar patient population. If an active infection is suspected, patients will be cultured and treated with appropriate antibiotics.

Delayed Autoimmune Diseases

It is possible that delayed autoimmune disease(s) may develop as a result of injection with PEP_{IDH1M} vaccine. This means that the immune system may be stimulated to attack natural tissue in the body. Animal studies have reported the development of autoimmunity in the context of vaccination and recovery from lymphopenia. However, our current experience with peptide vaccination in glioma patients has not demonstrated evidence of autoimmunity in treated patients. Furthermore, the doses of TMZ used in this study for induction of lymphopenia are standard doses administered to patients with gliomas. It therefore, is unknown what the risk of delayed autoimmune disease is for this study.

Phlebotomy

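### Autoimmune disease starting more than 1 to 2 months after the last vaccine is not systematically recorded, although the protocol names it as a delayed vaccine risk of unknown size

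*Combined protocol and SAP*

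**What the plan says.** **The risk.** Section 12.8.2 has its own heading for it: "It is possible that delayed autoimmune disease(s) may develop as a result of injection with" the vaccine. The paragraph cites animal reports of autoimmunity after vaccination during recovery from lymphopenia, and ends: "It therefore, is unknown what the risk of delayed autoimmune disease is for this study". Section 7.3.1 gives the same mechanism, and Section 7.2.6 says that the peptide has not been given to humans before.

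**The collection window.** Section 9.1: "All Adverse Events will be collected from time of consent until the end of the treatment phase of the study". It places the end of that phase 1 month after the last vaccine. Section 13.1 likewise stops AE recording at the End of Treatment visit. Section 12.3 ends the phase at 1 month or, after progression, once the immune-monitoring blood has been drawn, whichever is first. Section 9.6 differs: "End of study is defined as 2 months following last vaccine for purposes of toxicity monitoring".

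**The delayed-toxicity visit.** Section 12.2: "Subjects will return one month following the last vaccine for blood work (CBC and CMP) and clinical assessment to monitor for delayed toxicity". Table 2, footnote 3, repeats it with a physical examination.

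**After the window.** Section 9.1: "Patients will be followed only for overall survival, progression-free survival, and subsequent therapies thereafter". Section 12.4 lists the same three items. Section 9.3 adds: "Patients will be followed until death".

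**The concern.** Safety is the primary objective of a first-in-human study, and the protocol itself identifies a vaccine effect that may appear late. Follow-up continues until death and already records progression and later treatments, but it is expressly restricted to items that do not include a new autoimmune disease. The cut-off is tied to the last dose received, so it falls earliest for patients who stop or progress early.

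What is at stake is how a finding of no delayed autoimmunity would be read. Unless the report says that later onset was not solicited, readers may take an absence of records as an absence of disease.

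**Working it through.** The plan states no figure on this point, so there is nothing to reproduce. The check is how long AE collection lasts, and what the number of patients could show.

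**Inputs from the documents**
- Vaccine #1 on day 1, vaccine #3 on day 29, surgery 7 to 12 days later, so days 36 to 41 (Section 9.1; the ±3-day tolerances are ignored).
- Stable grade: vaccines #4 to #15 on day 22 of twelve 28-day TMZ cycles (Table 2 footnotes).
- Higher grade: vaccines #4 to #6 before, during and at the end of RT, then #7 to #15 on day 22 of nine cycles (Section 9.1). RT lasts 6 to 7 weeks (Sections 18.4 and 18.5.1), with a break of 3 ± 1 weeks before TMZ resumes (Section 18.5.2).
- Up to 28 patients enrolled and treated (Section 15.4.2).

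**Assumption.** The interval from surgery to the first TMZ cycle or to RT is not fixed; 14 to 35 days is used.

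**Day of the last vaccine**
- Stable grade, vaccine #15: surgery day + interval + 21 + 11 × 28. Shortest: 36 + 14 + 21 + 308 = 379. Longest: 41 + 35 + 21 + 308 = 405.
- Higher grade, vaccine #15: surgery day + interval + RT + break + 21 + 8 × 28. Shortest: 36 + 14 + 42 + 14 + 21 + 224 = 351. Longest: 41 + 35 + 49 + 28 + 21 + 224 = 398.
- Stopping after vaccine #3: day 29.

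**Months of AE collection after vaccine #1**, as (last vaccine day + 30 or 60 − 1) / 30.44

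| Patient | 1-month rule | 2-month rule |
|---|---|---|
| Stable grade, 15 vaccines | 408/30.44 = 13.4 to 434/30.44 = 14.3 | 438/30.44 = 14.4 to 464/30.44 = 15.2 |
| Higher grade, 15 vaccines | 380/30.44 = 12.5 to 427/30.44 = 14.0 | 410/30.44 = 13.5 to 457/30.44 = 15.0 |
| Stops after vaccine #3 | 58/30.44 = 1.9 | 88/30.44 = 2.9 |

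Measured from the last dose, cover is 1 or 2 months for everyone, and can be shorter than 1 month after progression under Section 12.3.

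**What 28 patients could show.** The documents give neither a frequency nor an onset time for autoimmune disease. For an assumed probability p of onset after the window, with all 28 patients followed, the chance of at least one case is 1 − (1 − p)^28:
- p = 1%: 1 − 0.99^28 = 0.25
- p = 2%: 1 − 0.98^28 = 0.43
- p = 5%: 1 − 0.95^28 = 0.76

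Even with complete ascertainment, zero cases in 28 would leave a one-sided 95% upper limit of 1 − 0.05^(1/28) = 10.1%.

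**The case against.** The strongest reply is that delayed toxicity was considered. AE collection runs through every vaccination, so a fully treated patient is watched for a year or more, including the repeated TMZ and vaccine cycles to which the proposed mechanism points. A dedicated visit follows 1 month after the last dose. Section 12.8.2 adds that the investigators' experience with peptide vaccination in glioma patients showed no evidence of autoimmunity. On this view a longer window is a matter of preference, and late cases after RT, TMZ and further therapies would be hard to attribute.

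Much of this stands, and it rules out several stronger readings that a reader might infer:
- **That no stated window could show the risk.** Onset during treatment, or by the 1-month visit, would be recorded.
- **That every later case would be missed.** Section 13.2.1 asks for immediate reporting of all SAEs and sets no end date, so a serious case known to the team could still be reported. A fatal case would appear as a death.
- **That this is the only delayed risk named.** Section 12.8.2 also describes radiation effects months or years later and possible TMZ carcinogenicity. Autoimmunity is the one headed as a delayed vaccine risk.
- **That the plan will publish a false zero.** No analysis in Section 15 reports a late autoimmune rate. The problem is one of interpretation.

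What the reply does not supply is any contact after the window at which such events are sought. The 1-month visit consists of CBC, CMP and a clinical assessment, with no AE assessment planned after it.

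**Conclusion.** The point holds as a limited gap in ascertainment, worth closing because closing it is cheap. Vaccine-related autoimmune disease that starts after the window is not systematically captured; cover beyond the last dose is 1 month (Sections 9.1, 12.3 and 13.1) or 2 months (Section 9.6). From first dose, that means about 12 to 15 months for a fully treated patient, but about 2 to 3 months for one who stops after vaccine #3. The primary percentage is not put in doubt; the affected conclusion is any statement about delayed autoimmunity.

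The 12-to-15-month range rests on the assumed interval after surgery. The probabilities of 0.25, 0.43 and 0.76 are illustrative: they rest on assumed rates and on all 28 patients being vaccinated and followed. The finding itself does not depend on any rate.

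**What to change.** In Sections 9.1 and 12.4, add two items to the existing OS, PFS and therapy follow-up: new autoimmune disease, and any SAE at least possibly related to vaccine, each with onset date. Report them descriptively and separately from the primary percentage, with the number of patients and the follow-up time covered. Section 12.5 sets the safety analysis at one month after the last enrolled subject's final vaccine, so give the data cut-off and add later cases in a dated update. Reconcile the 1-month and 2-month toxicity windows, and the earlier closure that Section 12.3 allows after progression with the visit that Section 12.2 requires. If the items are not added, the report should say that later onset was not solicited.

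The cost is an extra item on the follow-up CRF, with no new test. The protocol gives no schedule for follow-up contacts, so the item would go on whatever contact already collects progression and therapies. Ascertainment will be incomplete: Section 12.6.2 follows voluntary withdrawals only with permission, and patients withdrawn by the PI for survival alone. Attribution after RT, TMZ and later therapies will be limited, which is a further reason to keep the reporting descriptive.

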9.1.1 Definition of Unacceptable Toxicity

Toxicities will be graded according to the NCI CTCAE version 4 criteria. An unacceptable toxicity is defined as any Grade 3 toxicity at least possibly attributed to the vaccine (or vaccine + TMZ +/- RT) that does not resolve to baseline within 3 weeks, any Grade 3 hypersensitivity reactions requiring steroids, any Grade 4 toxicity, including neurologic events not due to progressive disease, or any life–threatening event not attributable to concomitant medication, co-morbid event, or disease progression.

Please refer to the Potential Risks Section 12.8.2 of this protocol.

